5.2. Clinical Experience

5.2.1 Phase 1 Studies

5.2.2 Phase 2 Studies

For SAD, 2 double-blind, randomized, placebo-controlled Phase 2 clinical studies (PH94B-CL016 and -CL022) included a total of 91 female subjects who met criteria for SAD (generalized subtype) as defined by the Diagnostic and Statistical Manual of Mental Disorders, 4th edition. PH94B (1.6 µg) was administered i.n. [REDACTED] to both a performance (public speaking) challenge and a social interaction challenge simulation which took place at the clinical sites. [REDACTED]

[REDACTED] The primary outcome measures were the Clinical Global Impression Scale - Improvement (CGI-I) and the Subjective Units of Distress Scale (SUDS). SUDS scores range from zero to 100, with higher scores indicating greater levels of anxiety. Subjects receiving PH94B were more likely than those who received placebo to show improvement on the CGI-I following treatment. In the PH94B group, 34 of 45 subjects (75.6%) were rated very much improved or much improved compared to only 17 of 46 subjects (37%) in the placebo group. A test for the difference between proportions indicated a Z value of 4.03, $p = 0.0001$ (Fisher's exact test).

During the public speaking challenge, subjects randomized to PH94B ($n = 45$) showed an improvement of 26.7 points in the mean SUDS score at Visit 3 (initial treatment visit) as compared to Visit 2 (Baseline, at which all subjects received placebo). In comparison, subjects randomized to placebo ($n = 46$) showed an improvement of only 14.0 points in the mean SUDS score across visits. The PH94B group's improvement from Visit 2 to Visit 3 significantly exceeded the placebo group's improvement from Visit 2 to Visit 3 ($t = 3.16$, $p = 0.002$) on this challenge. No SAEs were reported, and no subjects were terminated prematurely from the study due to AEs.

5.3. Summary of Potential Risks and Benefits

The potential benefits of study participation are that subjects with AjDA may experience a reduction in their symptoms when they encounter anxiety-provoking situations in daily life as a result of treatment with PH94B. No other benefits of participation are anticipated.

Based on previous clinical studies conducted with PH94B, it is believed to be safe and well tolerated, and risks to subjects are considered minimal. Intranasal administration of PH94B may increase the risk of local site reactions including itching, burning, runny nose, sneezing and soreness inside the nose. In completed clinical studies, the most commonly reported AE was headache. None of these effects was reported in more subjects receiving PH94B than in subjects receiving placebo. In a nonclinical long-term safety study, no toxic effects were observed in rats administered repeated daily doses of PH94B for 6 months, suggesting that prolonged exposure to PH94B is safe; no toxic effects are expected with prolonged exposure in humans.

A summary of the pharmaceutical properties and known potential risks of PH94B is provided in the current version of the investigator brochure (IB). The Investigator must become familiar with all sections of the PH94B IB before the start of the study.

6. OBJECTIVES

6.1. Primary Objective

The primary objective of this Phase 2a study is to evaluate the efficacy of PH94B Nasal Spray (PH94B) administered 4 times per day over 4 weeks for the treatment of anxiety in adult subjects with AjDA.

6.2. Secondary Objectives

The secondary objective of the study is to evaluate the safety and tolerability of PH94B.

6.3. Exploratory Objective

An exploratory objective of the study is to evaluate efficacy PH94B over time during the 4-week treatment period.

6.4. Endpoint Mapping

Objectives	Endpoints

Primary
 
The primary objective of this Phase 2a study is to evaluate the efficacy of PH94B administered 4 times per day over 4 weeks for the treatment of anxiety in adult subjects with AjDA.
	
The primary efficacy endpoint of the study is change from baseline in anxiety level as measured by the HAM-A at the end of the 4-week treatment period.
 
Secondary efficacy endpoints of the study include the following:
 
Individual subject improvement as assessed by the CGI-I. Values for comparison will be the proportion of “responders” in each group, defined as subjects receiving scores of 1 (Very much improved) or 2 (Much improved) at end of treatment with PH94B.
 
Individual subject improvement as assessed by the subject's self-assessment of improvement (by PGI-C) at the end of treatment compared to baseline. Values for comparison will be the proportion of “responders” in each group, defined as subjects receiving scores of 1 (Very much improved) or 2 (Much improved) at end of treatment with PH94B.
 
Individual subject improvement on the ADNM scale at the end of treatment compared to baseline.
 
Individual subject improvement on the IADQ at end of treatment compared to baseline.

Objectives	Endpoints
Secondary The secondary objective of the study is to evaluate the safety and tolerability of PH94B.	Incidence and severity of AEs, AEs leading to discontinuation, and SAEs. Changes in clinical laboratory values. Changes in 12-lead ECG results. Changes in physical examination findings. Changes in vital signs results. Changes in MADRS scores. Changes in suicidal ideation, as documented using the C-SSRS.
[REDACTED]	[REDACTED]
[REDACTED]	[REDACTED]

7. STUDY DESIGN

7.1. Overall Study Design and Plan

The study is a Phase 2a, double-blind, placebo-controlled, parallel study of i.n. PH94B versus placebo in 40 adult subjects with AjDA as defined by the DSM-5.

Subject participation in the study will last a total of 6 to 10 weeks, depending on the duration of the screening period and intervals between visits. Upon signing an informed consent, all subjects will complete Visit 1 (Screening) and enter a screening period lasting 7 to 35 days and includes a taper of concomitant anxiolytics, if necessary. As this protocol requires patients to be free of benzodiazepine anxiolytics for 30 days prior to baseline, the maximum screening period accounts for both a taper period and a 30 day benzodiazepine-free period if needed. The Screening visit will consist of safety assessments and psychiatric assessments to determine eligibility. After the screening period, eligible subjects will then return to complete Visit 2 (Baseline). If the subject continues to meet inclusion and exclusion criteria after review of psychiatric scales and laboratory results, the subject will be randomized 1:1 to receive 4 weeks of either PH94B or placebo administered 4 times daily. The subject will be trained on using the investigational product (IP) and it will be dispensed in 2 vials.

Subjects will return for weekly site visits (Visits 3, 4, and 5), in which the subject will return the IP vials dispensed at the previous visit and receive 2 new vials. Concomitant medications and AEs will be recorded. During these visits, the Hamilton Anxiety Scale (HAM-A), Patient Global Impression of Change (PGI-C), CGI-I Scale, Clinical Global Impression - Severity (CGI-S), and Columbia-Suicide Severity Rating Scale (C-SSRS) will be completed. Vital signs will be collected, and nasal passages will be examined.

When the subject returns for Visit 6, besides the assessments completed at Visits 3 through 5, the subjects will complete the Adjustment Disorder New Module Scale (ADNM), International Adjustment Disorder Questionnaire (IADQ), and Montgomery-Asberg Depression Rating Scale (MADRS) and have a physical examination, electrocardiogram (ECG), laboratory tests (chemistry and blood), urinalysis, urine drug screen, and urine pregnancy test. Any remaining IP vials will be collected. The subject will then come back after a 1-week washout period for the Follow-up visit (Visit 7). The HAM-A, C-SSRS, and the 20-item Physician Withdrawal Checklist (PWC-20) will be completed and any changes in AEs and concomitant medications from the last visit will be collected.

For each visit following Baseline (Visit 2), a ± 2 -day window will be allowed.

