	
9. Negative COVID-19 test for subjects with COVID-19 symptoms or who have had direct exposure to someone with a positive COVID-19 test, as determined by the Investigator.
 
Exclusion criteria:
 
1. Any history of schizophrenia or schizoaffective disorder.2. Any other current Axis I disorder, including, but not limited to, major depressive disorder, bipolar disorder, post-traumatic stress disorder, obsessive-compulsive disorder, premenstrual dysphoric disorder, and generalized anxiety disorder, which is in poor control and the primary focus of treatment.3. A diagnosis of social anxiety disorder.4. A score >60 on the LSAS at Screening (Visit 1).5. Subjects who meet criteria for moderate or severe alcohol or substance use disorder within 1 year prior to study entry.6. In the opinion of the Investigator, the subject has a significant risk for suicidal behavior during their participation in the study, or
a. At Screening (Visit 1): the subject scores "yes" on items 4 or 5 in the Suicidal Ideation section of the Columbia-Suicide Rating Scale (C-SSRS) with reference to a 6-month period prior to screening; orb. At Screening (Visit 1): the subject has had one or more suicidal attempts with reference to a 2 -year period prior to screening; orc. At Baseline (Visit 2): the subject scores "yes" on items 4 or 5 in the Suicidal Ideation section of the C-SSRS with reference to screening; ord. The subject is considered to be an imminent danger to themselves or others.7. Clinically significant nasal pathology or history of significant nasal trauma, nasal surgery, total anosmia, or nasal septum perforation that may have damaged the nasal chemosensory epithelium.8. An acute or chronic condition, including an infectious illness, uncontrolled seasonal allergies at the time of the study, or significant nasal congestion that potentially could affect drug delivery to the nasal chemosensory epithelium. The Investigator may allow concomitant use of over-the-counter nasal decongestants as needed, since there is no apparent drug interaction between these and PH94B.9. Concomitant use of any anxiolytics, such as benzodiazepines, buspirone, or cannabinoids during the study and within 30 days of Baseline (Visit 2).10. Concomitant use of any over-the-counter, prescription product, or herbal preparation for treatment of the symptoms of anxiety during the study and within 30 days before study entry. Selective serotonin reuptake inhibitors, serotonin-norepinephrine reuptake inhibitors, or other approved antidepressants are permitted if the dose has been stable for 30 days prior to Baseline (Visit 2).11. Women who have a positive urine pregnancy test prior to IP administration or are currently breast feeding.12. Subjects with clinically significant abnormalities in hematology, blood chemistry, urinalysis, ECG, or physical examination identified at the Screening visit that in the clinical judgment of the Investigator, could place the subject at undue risk, interfere with study participation, or confound the results of the study.13. Subjects with a positive urine drug screen at either Screening (Visit 1) or Baseline (Visit 2).14. Any current clinically significant and/or uncontrolled medical condition, based on medical history or as evidenced in screening assessments, such as COVID-19, HIV, cancer, stroke, congestive heart failure, uncontrolled diabetes mellitus, or any other medical condition or disease that, in the clinical judgment

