8.2.2 Exclusion Criteria

To be considered eligible for entry into the study, a subject must not meet any of the following exclusion criteria:

1. Any history of schizophrenia or schizoaffective disorder.

2. Any other current Axis I disorder, including, but not limited to, major depressive disorder, bipolar disorder, post-traumatic stress disorder, obsessive-compulsive disorder, premenstrual dysphoric disorder, and generalized anxiety disorder, which is in poor control and the primary focus of treatment.
3. A diagnosis of SAD.
4. A score >60 on the Liebowitz Social Anxiety Scale (LSAS).
5. Subjects who meet criteria for moderate or severe alcohol or substance use disorder within 1 year prior to study entry.
6. In the opinion of the Investigator, the subject has a significant risk for suicidal behavior during their participation in the study, or
 - a. At Screening (Visit 1): the subject scores “yes” on items 4 or 5 in the Suicidal Ideation section of the C-SSRS with reference to a 6-month period prior to screening; or
 - b. At Screening (Visit 1): the subject has had one or more suicidal attempts with reference to a 2 year period prior to screening; or
 - c. At Baseline (Visit 2): the subject scores “yes” on items 4 or 5 in the Suicidal Ideation section of the C-SSRS with reference to screening; or
 - d. The subject is considered to be an imminent danger to themselves or others.
7. Clinically significant nasal pathology or history of significant nasal trauma, nasal surgery, total anosmia, or nasal septum perforation that may have damaged the nasal chemosensory epithelium.
8. An acute or chronic condition, including an infectious illness, uncontrolled seasonal allergies at the time of the study, or significant nasal congestion that potentially could affect drug delivery to the nasal chemosensory epithelium. The Investigator may allow concomitant use of over-the-counter nasal decongestants as needed, since there is no apparent drug interaction between these and PH94B.
9. Concomitant use of any anxiolytics, such as benzodiazepines, buspirone, or cannabinoids during the study and within 30 days of Baseline (Visit 2).

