10. Concomitant use of any over-the-counter, prescription product, or herbal preparation for treatment of the symptoms of anxiety during the study and within 30 days before study entry. Selective serotonin reuptake inhibitors, serotonin-norepinephrine reuptake inhibitors, or other approved antidepressants are permitted if the dose has been stable for 30 days prior to Baseline (Visit 2).
11. Women who have a positive urine pregnancy test prior to IP administration or are currently breast feeding.
12. Subjects with clinically significant abnormalities in hematology, blood chemistry, urinalysis, electrocardiogram, or physical examination identified at Screening(Visit 1) that in the clinical judgment of the Investigator, could place the subject at undue risk, interfere with study participation, or confound the results of the study.
13. Subjects with a positive urine drug screen at either Screening(Visit 1) or Baseline(Visit 2).

14. Any current clinically significant and/or uncontrolled medical condition, based on medical history or as evidenced in screening assessments, such as COVID 19, HIV, cancer, stroke, congestive heart failure, uncontrolled diabetes mellitus, or any other medical condition or disease that, in the clinical judgment of the Investigator, could place the subject at undue risk, interfere with study participation, or confound the results of the study.
15. Use of a concomitant medication that, in the clinical judgment of the Investigator, could place the subject at undue risk, interfere with study participation, or confound the results of the study.
16. History of cancer or malignant tumor not in remission for at least 2 years. Basal cell skin cancers are not exclusionary.

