- Obtain urine sample for urine drug screen: Instant Exam to be performed on site, with results thoroughly documented in the source
- For females of childbearing potential, obtain urine sample and complete on-site urine pregnancy test. If positive, a serum pregnancy test should be conducted
- Administer LSAS
- Administer MADRS
- Administer HAM-A
- Administer C-SSRS
- Administer CGI-S
- Review all inclusion and exclusion criteria

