10.2.2 Baseline (Visit 2)

For subjects continuing to meet all eligibility criteria, the following assessments will be completed at Baseline (Visit 2):

- Subject to fill out ADNM
- Administer MADRS
- Administer HAM-A

- Administer C-SSRS (since last visit)
- Administer CGI-S
- Administer IADQ
- Measure vital signs after the subject has rested for 5 minutes: seated systolic and diastolic blood pressure, heart rate, respiratory rate, and body temperature
- Obtain blood and urine samples for clinical laboratory examination, including hematology, chemistry, prolactin, thyroid functioning, and urinalysis (refer to Section 10.3.2.1.1 for complete list)
- Obtain urine sample for urine drug screen: Instant Exam to be performed on site, with results thoroughly documented in the source
- For females of childbearing potential, obtain urine sample and complete on-site urine pregnancy test
- Record concomitant medication use including the completion of any washout
- Review all inclusion and exclusion criteria

For subjects meeting all study inclusion criteria and no study exclusion criteria, (after review of the assessments above) the following Visit 2 procedures will be performed:

- Randomize the subject and obtain first IP vial
- Train subjects on use of IP and dosing
- Prior to giving a vial(s) to the subject, site staff will identify/mark the vials as vial #1 and vial #2. Staff will then instruct the subject on initial priming and ongoing priming, as outlined in the Study Manual
- Both IP vials will be weighed (as per instructions in the Study Manual). The subject will then complete the initial priming and self-administer the first dose in the presence of site personnel
- Record any AEs reported after IP administration

The next visit (Visit 3) will be scheduled 1 week (± 2 days) after the date of Baseline (Visit 2).

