10.3.2.1 Clinical Laboratory Safety Assessments

10.3.2.1.1 Clinical Laboratory Tests to be Performed

Samples for the following laboratory tests will be collected at the time points specified in the schedule of events (Table 2-1).

All laboratory tests will be performed on site during the study, and include the following:

Chemistry Panel:	alanine aminotransferase, aspartate aminotransferase, albumin, calcium, chloride, alkaline phosphatase, bicarbonate, cholesterol, creatine kinase, creatinine, direct bilirubin, lactate dehydrogenase, magnesium, globulin, glucose, gamma-glutamyl transferase, indirect bilirubin, phosphorous, potassium, sodium, total bilirubin, total protein, triglycerides, urea nitrogen, uric acid
Hematology/ Hemogram Panel:	hematocrit, hemoglobin, mean corpuscular hemoglobin, mean corpuscular concentration, mean corpuscular volume, platelets, red blood cell count, white blood cell count, red blood cell morphology
Hematology Differential Panel:	basophils, eosinophils, lymphocytes, monocytes, neutrophils
Urinalysis macroscopic panel:	bilirubin, blood, clarity, color, glucose, ketones, leucocyte esterase, nitrite, pH, protein, specific gravity, urobilinogen
Urine Pregnancy Test:	for all female subjects of childbearing potential
Urine Drug Screen:	tricyclic antidepressants, opiates, cocaine, benzodiazepines, amphetamines, barbiturates, cannabinoids, methadone, methamphetamine, phencyclidine, propoxyphene, buprenorphine, ecstasy, oxycodone

- Other:
 - prolactin
 - thyroid stimulating hormone
 - free thyroxine (T4) (if thyroid stimulating hormone is above the upper or below the lower normal limits, then free thyroxine will automatically be performed)

The local laboratory should be used for any unscheduled and follow-up labs, if needed. This includes any confirmatory pregnancy or drug screens for positive urine tests. Additional urine and blood samples may be collected for further evaluation of safety as warranted by the Investigator's judgment.

Results and reports from the local laboratory should be filed with the source documents for each subject. The local laboratory will provide results to the study site staff as soon as they are available and will be provided to sponsor or designated data manager within agreed timelines.

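### Exclusion 13 shuts out a benzodiazepine user who tests positive at Visit 1, although Sections 7.1 and 10.2.1.2 provide a taper and 30-day washout for that same subject

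*Protocol*

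**What the plan says.** **The washout path.** Protocol 7.1 describes a screening period of 7 to 35 days that can include a taper of anxiolytics, and states that "the maximum screening period accounts for both a taper period and a 30 day benzodiazepine-free period if needed". Section 10.2.1.2 gives benzodiazepines as its example of a drug to be stopped 30 days before Baseline. Sections 9.7.2 and 10.2.1.1 support this in general terms: 9.7.2 leaves taper rates to the investigator and requires consent before any taper, and 10.2.1.1 lets screening run to 35 days when a taper is needed. Those two sections speak of prohibited medications; they neither name benzodiazepines nor state the 30 days.

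**The exclusion.** Exclusion 13 in 8.2.2 reads "Subjects with a positive urine drug screen at either Screening(Visit 1) or Baseline(Visit 2"; the synopsis has the same rule: "Subjects with a positive urine drug screen at either Screening (Visit 1) or Baseline (Visit 2". Neither carries an exception.

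**The test.** The panel in 10.3.2.1.1 begins "tricyclic antidepressants, opiates, cocaine, benzodiazepines, amphetamines, barbiturates, cannabinoids, methadone". At Visit 1 the instruction is "Obtain urine sample for urine drug screen: Instant Exam to be performed on site, with results thoroughly documented in the source".

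**The second look.** The Visit 2 procedures include "Review all inclusion and exclusion criteria".

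**The neighbouring criterion.** Exclusion 9 counts from Baseline: "Concomitant use of any anxiolytics, such as benzodiazepines, buspirone, or cannabinoids during the study and within 30 days of Baseline (Visit 2". On that criterion, a benzodiazepine user at Visit 1 can qualify after washout.

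**The concern.** The protocol gives two instructions for one patient. A site that works from exclusion 13 records a screen failure at Visit 1. A site that works from 7.1 and 10.2.1.2 starts a taper. The second course is the more troubling for the patient: a benzodiazepine is withdrawn for a study that exclusion 13 does not let the patient enter, and 9.7.2 itself recognizes that washout can leave a subject clinically unstable. If the patient is randomized anyway, that is an eligibility violation, which SAP 7.2 lists among its examples of important deviations.

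**Working it through.** This is a check of text and logic. No sample size or error rate enters.

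**Timeline first.** Inputs: screening of 7 to 35 days, 4 weeks (28 days) of treatment, and about 1 week (7 days) of follow-up (Protocol 7.1 and 10.1).
- Shortest: (7 + 28 + 7) / 7 = 6 weeks.
- Longest: (35 + 28 + 7) / 7 = 10 weeks.

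Both match the 6 to 10 weeks stated in 7.1, so the 35-day maximum is built into the stated study length.

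**Is the subject on the drug when tested?** Consent and the urine drug screen are both on the Visit 1 list in 10.2.1.1. Sections 9.7.2, 10 and 10.2.1.1 all put consent before any taper. A subject who needs the taper has therefore not begun it under the protocol when the Visit 1 sample is taken.

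**Apply exclusion 13.** As written, a subject is excluded if Visit 1 is positive OR Visit 2 is positive. The last column uses the wording proposed under the fix.

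| Subject at Visit 1 | Visit 1 screen | Visit 2 screen | As written | After the change |
|---|---|---|---|---|
| Prescribed benzodiazepine, then washed out | positive | negative | excluded | not excluded |
| Prescribed benzodiazepine, washout not achieved | positive | positive | excluded | excluded |
| Prescribed benzodiazepine, below detection | negative | negative | not excluded | not excluded |
| Buspirone (not on the panel), no panel drug | negative | negative | not excluded | not excluded |

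The conflict is the first row: the subject does what 7.1 and 10.2.1.2 ask, is clean at Baseline, and is still excluded.

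**Look for a way out in the legible text.**
- *Repeat test.* 10.3.2.1.1 allows an abnormal result to be repeated, and positive urine tests to be confirmed locally. Both serve to verify a finding; neither waives a true positive.
- *Rescreening.* 14.3 does not allow it.
- *A clean Visit 2.* Exclusion 13 applies to either visit and all criteria are reviewed again at Visit 2, so the earlier positive still counts.
- *Intended only for illicit use.* The text does not say so, and the panel includes prescribed classes.
- *Discretion.* 8.2 bars enrollment of anyone who fails a criterion.

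**The case against.** The best reply is that exclusion 13 is clear, is worded alike in both places, and is checked on the spot. A site that follows it will screen-fail the subject at Visit 1 and no harm follows. Section 9.7 also tells sites to ask the Medical Monitor when unsure about a concomitant medication. Some of this stands: divergence between sites is a risk, not an established fact. But strict application of exclusion 13 defeats the provision in 7.1 for any user who tests positive, and 9.7 gives the Medical Monitor no stated power to waive an exclusion.

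The evidence also has limits. The schedule of events is not shown, and the synopsis line on screening and washout and the screening length in SAP 3.2 are redacted. The point rests on what can be read, and both sides of the conflict can be.

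A reader might infer more than the documents support:
- *A recruitment shortfall.* No prevalence of benzodiazepine use is given, so no number of lost candidates can be derived. Some users would fail for other reasons, for instance because they become unstable on washout.
- *Closure of the whole washout path.* Users who test negative, and users of off-panel drugs such as buspirone, keep it.
- *A known effect on the analysis sets.* SAP 5 and 7.2 take deviations into account when populations are settled at blinded review, so the place of such a subject cannot be stated in advance.
- *An error in the time allowed for tapering.* The text leaves 35 − 30 = 5 days. That is short, but not contradictory.
- *A second bar in exclusion 10.* It refers to use "for treatment of the symptoms of anxiety during the study and within 30 days before study entry" and does not define that entry point. Since 14.3 describes screen failures as consented subjects who never entered, Baseline is the more natural reading, and the conflict then disappears.
- *A bar on the taper in 9.7.2.* Its first sentence prohibits psychotropics from Visit 1, but the same section goes on to provide the washout. This is loose drafting that needs a conforming edit.

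**Conclusion.** The conflict is real and exclusion 13 is wrong as written. A benzodiazepine user who tests positive at Visit 1 is ineligible, while 7.1 and 10.2.1.2, supported by the general taper text in 9.7.2 and 10.2.1.1, provide a route into the study for that subject. The effect is confined to eligibility, consistency between sites, and the possibility of a needless taper. Its size in subjects is unknown. No effect on power, analysis populations, the primary analysis or bias between arms is shown. The conclusion assumes that the redacted or missing pages hold no exemption, and it applies only to subjects who actually test positive. It should be fixed, because the correction is small and the present wording can lead to treatment being withdrawn to no purpose.

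**What to change.** Reword exclusion 13 in both the synopsis and 8.2.2, for example:

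> *A positive urine drug screen at Visit 2; or a positive urine drug screen at Visit 1 for any drug other than a prescribed benzodiazepine that will be tapered and washed out under Sections 9.7.2 and 10.2.1.2.*

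This keeps the negative screen at Visit 2 as the safeguard.

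State explicitly whether a Visit 1 cannabinoid positive excludes. Exclusion 9 counts cannabinoids among the anxiolytics, so the general washout text could be read to cover them, whereas the wording above would exclude them. Either answer is workable, but it should be the sponsor's stated choice.

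As a conforming edit, add two exceptions to the first sentence of 9.7.2: a drug being tapered before Baseline, and the antidepressants that exclusion 10 permits.

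The cost is wording in three places of one protocol amendment, with the usual IRB approval. Visits, screening limits, sample size and analysis do not change.
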